9.6 Administration

Study drug will be administered as follows:

- Doses for the 5 VX-150 treatment arms are shown in Table 9-1. The total maximum daily dose will not exceed 2250 mg (1500 mg loading dose followed by doses of 750 mg q12h).
- VX-150 arms will receive a combination of VX-150 and VX-150 placebo capsules.
- Placebo arm will receive only VX-150 placebo.
- To maintain the blind, all subjects will receive the same number of capsules. All subjects will receive 6 capsules for the first dose and 4 capsules for the remainder of the dosing period. Additional details on dispensing will be included in the Pharmacy Manual.

- Study drug will be administered as described above, with the final dose of VX-150 or VX-150 placebo given 36 hours after the first dose.
- Study drug will be administered orally with approximately 240 mL (8 fluid ounces) of water.
- Subjects will swallow the study drug whole and will not chew the drug before swallowing.
- Study drug must be administered following the food restrictions outlined in Section 9.4.2.

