11.4 Efficacy

Pain scales: After removal of the popliteal sciatic block, a subject can be randomized once the subject requests the first dose of study drug for pain relief, and the subject's pain is ≥4 on the NPRS and is moderate or severe on the VRS. If a subject does not meet the NPRS and VRS criteria within 9 hours of removal of the popliteal sciatic block, the subject will not be eligible for the study.

Subjects will report their pain on the NPRS at scheduled time points (Table 3-2) through 48 hours after the first dose of study drug. In addition, pain intensity will be recorded on the NPRS scale immediately before each administration of rescue medication.

When NPRS assessments coincide with collection of PK blood samples, the NPRS assessment will be performed first.

Double-stopwatch assessment: At the time of first dose, 2 stopwatches will be started: 1 labeled "perceptible pain relief" and the other labeled "meaningful pain relief." Subjects will stop the "perceptible pain relief" stopwatch when/if they feel any pain relief at all and stop the "meaningful pain relief" stopwatch when/if they feel relief that is "meaningful" to them. If the subject does not stop both stopwatches by 6 hours after the first dose, or receives rescue medication, the stopwatches will be stopped.

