7 STUDY DESIGN

7.1 Overall Design

This is a Phase 2B randomized, double-blind, placebo-controlled, dose ranging, 6-arm, parallel-design study. Subjects will receive a primary unilateral first metatarsal bunionectomy repair on Day -1 (Figure 7-1). A continuous popliteal sciatic block infusion (0.2% ropivacaine) will be started after surgery and will be removed between 3AM and 5AM on Day 1. After removal of the popliteal sciatic block, a subject can be randomized once the subject requests the first dose of study drug for pain relief, and the subject's pain is ≥4 on the NPRS and is moderate or severe on the VRS (Verbal Categorical Rating Scale). If a subject does not meet the NPRS and VRS criteria within 9 hours of removal of the popliteal sciatic block, the subject will not be eligible to enroll in the study.

A total of approximately 242 subjects will be randomized 2:2:2:2:1:2 to 6 treatment arms, evaluating a range of 5 VX-150 dose levels as shown in Table 7-1.

Table 7-1 VX-150 Doses by Treatment Arm

Treatment	Dose Level	Dose	Number of Subjects
VX-150	1 (highest)	First dose 1500 mg, then 750 mg q12h	44
	2	1000 mg qd	44
	3	500 mg q12h	44
	4	First dose 500 mg, then 250 mg q12h	44
	5 (lowest)	250 mg qd	22
Placebo			44

[figure not shown]
q12h: every 12 hours; qd: daily

Note: q12h dosing will be through 36 hours after the first dose of study drug throughout the protocol.

Subjects will report their pain on the NPRS at scheduled time points (See Table 3-2 in CSP) through 48 hours after the first dose of study drug. In addition, pain intensity will be recorded

on the NPRS immediately before each administration of rescue medication. Subjects are encouraged to wait 90 minutes after the first dose of study drug to receive rescue medication, and subjects should generally not receive rescue medication unless their NPRS is ≥4. However, subjects may receive rescue medication at any time after the first dose of study drug per their request. The rescue medication will be ibuprofen (400 mg [oral] every 4 hours [q4h] as needed [prn]).

Figure 7-1 VX18-150-104 Study Design

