9.3.1.2 Primary Analysis

The primary efficacy analysis will be using the MCP-Mod approach to detect the dose-response relationship from a candidate set of 4 dose-response models (Linear, Emax, Logistic, and Sigmoid Emax). Dose level 2 and Dose level 3 of VX-150 group will be combined into one treatment group in the MCP-Mod procedure. Total dose on Day 1 for each treatment group will be used in the MCP-Mod procedure as shown in Table 9-1.

Table 9-1 VX-150 Doses by Treatment in Primary Analysis

Treatment	Dose Level	Dose	Total Dose on Day 1	Analysis Treatment Group	
VX-150	First dose 1500 mg, then 750 mg q12h		2250 mg	VX-150 Dose Level 1	
	2	1000 mg qd	1000	VX-150 Dose Level 2/3	
	3 500 mg q12h		1000 mg	VA-130 Dose Level 2/3	
	4	First dose 500 mg, then 250 mg q12h	750 mg	VX-150 Dose Level 4	
	5 (lowest)	250 mg qd	250 mg	VX-150 Dose Level 5	
Placebo			0 mg	Placebo	

MCP-Mod approach will be based on an analysis of covariance (ANCOVA) model. The model will include SPID24 after the first dose as the dependent variable, treatment as a fixed effect, with site, sex, and baseline pain intensity score as covariates. The Least Squares (LS) means (SE) and 95% confidence interval (CI) will be provided for each treatment group. From the MCP-Mod procedure, the 2-sided *P* value will be provided for each dose-response model in the candidate set. If at least one dose-response model in the candidate set is statistically significant, a dose-response model will be selected based on the maximum test statistic criterion. The selected dose-response model will be estimated and presented in a figure.

Pain intensity scores used for the primary analysis will be summarized descriptively including SE by treatment at each scheduled time point and the mean values over time by treatment will be presented in a figure. SPID24 used for the primary analysis will also be summarized descriptively including SE by treatment.

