If the subject has not stopped the stopwatch by 6 hours after the first dose, the stopwatch will be stopped and time to onset will be considered censored at 6 hours. If the subject receives rescue medication during the first 6 hours, the stopwatch will be stopped immediately before administration of rescue medication and time to onset will be considered censored at the time of rescue medication plus 4 hours or at 6 hours, whichever happened earlier. If perceptible pain relief is obtained without associated meaningful pain relief, time to onset of "confirmed perceptible pain relief" will also be considered censored at 6 hours.

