9.3.2.2 Secondary Analyses

Time-weighted sum of the pain intensity difference between VX-150 versus placebo as recorded on a NPRS 0 to 48 hours (SPID48) after the first dose: Same imputation strategies as described for SPID24 in Section 9.3.1.1 will be applied to SPID48.

[figure not shown]
Proportions of subjects with at least 30%, 50%, or 70% reduction in NPRS at 24 hours after the first dose of VX-150 versus placebo: Analysis of responder rates between each individual dose level of VX-150 and placebo will be conducted using Cochran-Mantel-Haenszel test, stratified by site and sex.

Time to onset of "confirmed perceptible pain relief" and "meaningful pain relief" after the first dose of VX-150 versus placebo: Time to onset of "confirmed perceptible pain relief" will be analyzed using Cox regression model. The model will include treatment, site and sex as covariates. Pairwise comparison between each individual dose level of VX-150 and placebo will be conducted under the model.

Note: If placebo group has fewer than 5 subjects experience "confirmed perceptible pain relief", the Cox regression will not be performed. If any dose level of VX-150 group has fewer than 5 subjects experience "confirmed perceptible pain relief", the particular dose level group will not be included in the Cox regression model.

Additionally, the Kaplan-Meier method will be used to produce graphical presentation of the survival curves by treatment group.

Time to onset of "meaningful pain relief" and time to onset of "perceptible pain relief" will be analyzed in the same way as described for time to onset of "confirmed perceptible pain relief".

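### Dose Levels 3 and 4 are the same assigned treatment throughout the 6-hour stopwatch period, but SAP 9.3.2.2 compares each with placebo separately; pooling them by first dose would give a more precise onset comparison

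*SAP*

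**What the plan says.** **Regimens (SAP 7.1, Table 7-1; Protocol Table 9-1).** Dose Level 3 is 500 mg every 12 hours. Dose Level 4 is "First dose 500 mg, then 250 mg q12h". Each arm has 44 subjects, as does placebo.

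**Capsules (Protocol 9.6).** "All subjects will receive 6 capsules for the first dose and 4 capsules for the remainder of the dosing period". Active capsules are 250 mg, with matching placebo (Protocol 10.2).

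**Observation window (Protocol 11.4).** "If the subject does not stop both stopwatches by 6 hours after the first dose, or receives rescue medication, the stopwatches will be stopped". SAP 9.3.2.1 agrees: "If the subject has not stopped the stopwatch by 6 hours after the first dose, the stopwatch will be stopped". After rescue, "time to onset will be considered censored at the time of rescue medication plus 4 hours or at 6 hours, whichever happened earlier".

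**Onset analysis (SAP 9.3.2.2).** The Cox model has treatment, site and sex. "Pairwise comparison between each individual dose level of VX-150 and placebo will be conducted under the model". Confirmed perceptible, perceptible and meaningful relief are all handled this way. If an active dose level has fewer than 5 subjects with the event, "the particular dose level group will not be included in the Cox regression model".

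**Grouping elsewhere (SAP 9.3.1.2).** "Dose level 2 and Dose level 3 of VX-150 group will be combined into one treatment group in the MCP-Mod procedure". The stated basis is total dose on Day 1. The public SAP text gives no grouping by first dose for the onset endpoints.

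**The concern.** Onset is timed from the first dose and closes at 6 hours. Dose Levels 3 and 4 first differ at 12 hours. In this window the design therefore has four active first-dose levels (1500, 1000, 500 and 250 mg), while the planned model has five.

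Two things follow. The 500 mg first dose gets two noisier estimates where the data allow one better one. And any gap between the two arms in onset is chance, although the results table shows them as two dose levels. In a trial meant to inform Phase 3 dose selection, a significant result for one arm beside a non-significant result for its twin is awkward to interpret. The SAP applies no multiplicity adjustment outside MCP-Mod and sets no ordering that would settle such a split.

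**Working it through.** **1. The plan's own figures.** The documents give no power, event rate or hazard ratio for onset. The only pairwise figure is for SPID24: at least 85% power at effect size 0.7 with 40 evaluable per group. Normal approximation: Φ(0.7 × √(40/2) − 1.96) = Φ(1.17) = 87.9%, which agrees. The total also agrees: 5 × 44 + 22 = 242.

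**2. Are the arms identical up to 6 hours?**

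| | Dose Level 3 | Dose Level 4 |
|---|---|---|
| Hour 0 | 500 mg: 2 active + 4 placebo capsules | 500 mg: 2 active + 4 placebo capsules |
| Latest onset or censoring time | 6 h | 6 h |
| Hour 12 | 500 mg | 250 mg |

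The capsule split is derived from 500/250 = 2 active capsules out of 6. The rescue rule takes the earlier of rescue plus 4 hours and 6 hours, so it never goes past 6 hours. No other pair of arms shares a first dose.

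**3. Precision.** Take the variance of the log hazard ratio as 1/(active events) + 1/(placebo events).

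- Equal event fractions: SE ratio = √[(1/88 + 1/44)/(1/44 + 1/44)] = √0.75 = 0.866, a 13% reduction.
- With a drug effect, taking 50% placebo onset by 6 h and HR 1.8 (both assumed): placebo events are 44 × 0.5 = 22. The active fraction is 1 − 0.5^1.8 = 0.713, so 31.4 events in one arm and 62.7 pooled. Separate SE = √(1/31.4 + 1/22) = 0.278; pooled SE = √(1/62.7 + 1/22) = 0.248; ratio 0.89. A Cox simulation of this case gave median SEs of 0.280 and 0.249 (ratio 0.889), with power 57% separate and 68% pooled.

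Six-arm Cox simulations (2000 runs each, planned arm sizes, exponential onset, cut-off at 6 h, no site, sex or rescue effects):

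| Placebo onset by 6 h | HR, 500 mg | Power, Level 3 / Level 4 | Power, pooled | SE ratio | One significant, one not |
|---|---|---|---|---|---|
| 30% | 1.8 | 38% / 37% | 44% | 0.897 | 31% |
| 40% | 1.5 | 24% / 26% | 30% | 0.885 | 27% |
| 40% | 1.8 | 47% / 48% | 57% | 0.893 | 32% |

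**4. Power.** With single-arm power p (two-sided 5% assumed), z = 1.96 + Φ⁻¹(p), and pooled power = Φ(z/ratio − 1.96).

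| Single-arm power | Pooled, ratio 0.889 | Pooled, ratio 0.866 |
|---|---|---|
| 50% | 60% | 62% |
| 80% | 88% | 90% |

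The ratio 0.866 needs equal event counts per arm, so the 0.889 column is the better guide when the drug works.

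**5. Split results.** The two contrasts share placebo, so with equal information their test statistics correlate at 0.5. P(exactly one significant) = 2 × [p − P(both significant)]. At p = 50%, P(both) = 1/4 + arcsin(0.5)/(2π) = 1/3, so the split probability is 2 × (1/2 − 1/3) = 33.3%, the maximum. At p = 80% it is 22.6%; at 90%, 13.5%.

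**6. Fewer-than-5-events rule.** With k = P(fewer than 5 events among 44), the chance of dropping one arm and keeping its twin is 2k(1 − k). At a 10% event rate, k = 0.547 gives 50%; at 15%, k = 0.190 gives 31%; at 20%, k = 0.044 gives 8%. This matters only if onset is rare.

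**The case against.** The strongest reply is that this is an efficiency choice and not an error. Comparing each randomised arm with placebo is valid and unbiased, and it follows the FAS rule of analysis by randomised group. The responder analysis uses the same arm-by-arm layout. Onset is a secondary endpoint with no power claim and no success criterion. All of that stands.

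Several stronger readings are tempting, and the documents do not support them:

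- *A reader might infer that the SAP contradicts itself by pooling Dose Levels 2 and 3 but not 3 and 4.* The first pooling is stated for MCP-Mod, where arms sit on a numerical dose axis and those two share one value. The pairwise Cox model has no dose axis. The precedent is suggestive only.
- *A reader might infer that the SAP will report a Level 3 v Level 4 difference as a dose effect.* No such contrast and no dose-response model for onset appears in SAP 9.3.2.2. A false impression would come from how the table is read, and Table 7-1 shows both arms starting at 500 mg.
- *A reader might take split results to mean effects in opposite directions.* They mean significant v non-significant. Any two equally effective arms can split this way, and estimates with intervals soften it.
- *A reader might extend the point to SPID24, SPID48 or the 24-hour responders.* It does not extend there, because the 12-hour doses differ.

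What remains is that no stated reason favours keeping two identical treatments apart in this window, and pooling preserves the randomised comparison.

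**Conclusion.** The point holds as a cheap improvement to secondary endpoints. For all three stopwatch endpoints, Dose Levels 3 and 4 are one assigned treatment, and the plan estimates its effect twice with less precision than it could have once. Pooling lowers the standard error by about 10-13% (nearer 10-12% if the drug works), worth about 10 percentage points of power at 50% and about 8 at 80%. It also removes a split between identical arms that would otherwise arise in about 23-33% of trials at 50-80% single-arm power.

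That the treatments are identical is fixed by the documents. The sizes rest on assumed event rates and hazard ratios, a two-sided 5% level for the pairwise tests and the planned arm sizes. The planned contrasts are not biased, and the primary SPID24 analysis is unaffected.

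**What to change.** In SAP 9.3.2.2, before database lock:

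- Analyse perceptible, confirmed perceptible and meaningful relief in the FAS by **randomised (assigned) first dose**: placebo (44), 250 mg (22), 500 mg (Dose Levels 3 and 4, 88), 1000 mg (44) and 1500 mg (44). Keep site and sex as covariates and compare each group with placebo. Grouping by dose actually received would conflict with the FAS rule.
- Apply the fewer-than-5-events rule to the pooled 500 mg group.
- Show Kaplan-Meier curves by first-dose group so that they match the model, and keep the by-arm results as descriptive.
- State that Dose Levels 3 and 4 are not pooled on this basis for endpoints that extend beyond 12 hours.

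The cost is a few sentences of SAP text and no new data. The downside is one more grouping scheme to explain in the report, beside the randomised arms and the Dose Level 2/3 grouping used in MCP-Mod.

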12.3.3.2 Analysis of Secondary Efficacy Variables

- Time-weighted sum of the pain intensity difference between VX-150 versus placebo as recorded on a NPRS 0 to 48 hours (SPID48) after the first dose: analysis of this variable will be similar to the primary analysis.
- Proportions of subjects with at least 30%, 50%, or 70% reduction in NPRS at 24 hours after the first dose of VX-150 versus placebo: This variable will be analyzed using the Cochran-Mantel-Haenszel test, stratified by site and sex.
- Time to onset of "confirmed perceptible pain relief" after the first dose of VX-150 versus placebo: This variable will be analyzed using Cox regression model. The model will include a covariate for treatment and adjustment for site and sex. Additionally, the Kaplan-Meier method will be used to produce graphical presentation of the survival curves by treatment group and to estimate survival rates by treatment group.
- Time to onset of "meaningful pain relief" after the first dose of VX-150 versus placebo: The analysis of this variable will be similar to the analyses of time to onset of "perceptible pain relief."

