9.3.2 Analysis of Secondary Efficacy Variables

9.3.2.1 Definition of Secondary Efficacy Variables

Time-weighted sum of the pain intensity difference between VX-150 versus placebo as recorded on a NPRS 0 to 48 hours (SPID48) after the first dose: SPID48 will be calculated using the following formula:

 $\begin{array}{l} \bullet \quad SPID48 = 0.5 \times PID_{0.5} + 0.5 \times PID_1 + 0.5 \times PID_{1.5} + 0.5 \times PID_2 + PID_3 + PID_4 + PID_5 \\ + PID_6 + 2 \times PID_8 + 4 \times PID_{12} + 4 \times PID_{16} + 4 \times PID_{20} + 4 \times PID_{24} + 4 \times PID_{28} + 4 \times PID_{32} + 4 \times PID_{36} + 4 \times PID_{40} + 4 \times PID_{44} + 4 \times PID_{48} \end{array}$

Proportions of subjects with at least 30%, 50%, or 70% reduction in NPRS at 24 hours after the first dose of VX-150 versus placebo: A subject with at least 30%, 50%, or 70% reduction in NPRS at 24 hours after the first dose of study drug will be defined as a "responder". The percentage reduction in the NPRS will be calculated as following:

• 100 × (NPRS at baseline –NPRS at 24 hours) / NPRS at baseline

If a subject discontinues the study drug treatment for any reason prior to 24 hours, this subject will not be a "responder" for any of the three criteria. If a subject has missing NPRS at 24 hours without discontinuing the study drug treatment prior to 24 hours, the LOCF principle will be used to impute pain intensity score at 24 hours. The last observed pain intensity score should be from a regularly scheduled measurement including a previous prerescue assessment, but cannot be any actual measurements taken during a previous rescue period.

Time to onset of "confirmed perceptible pain relief" and "meaningful pain relief" after the first dose of VX-150 versus placebo: Time to onset of "perceptible pain relief" is the time elapsed from first dose of VX-150 or placebo until the subject stops the "perceptible pain relief" stopwatch. Time to onset of "meaningful pain relief" is the time elapsed from first dose of VX-150 or placebo until the subject stops the "meaningful pain relief" stopwatch. Time to onset of "confirmed perceptible pain relief" will be defined as the time to onset of perceptible pain relief for those subjects who had meaningful pain relief.

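### With fewer than 5 placebo onset events, the SAP drops every dose-versus-placebo comparison of time to onset and names no replacement test

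*SAP*

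**What the plan says.** Time to onset is a secondary efficacy endpoint in both documents (Protocol 7.2, SAP 6.1.2).

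Protocol 12.3.3.2 plans the analysis without any event-count condition: "This variable will be analyzed using Cox regression model", adjusted for site and sex. It adds Kaplan-Meier curves and uses the same method "to estimate survival rates by treatment group".

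SAP 9.3.2.2 keeps the Cox model with treatment, site and sex, and makes the pairwise dose-versus-placebo comparisons within it. It then adds two conditions, one on placebo and one on the active arms: "If placebo group has fewer than 5 subjects experience" confirmed perceptible relief, "the Cox regression will not be performed. If any dose level of VX-150 group has fewer than 5 subjects experience" it, "the particular dose level group will not be included in the Cox regression model". So a sparse placebo arm means no Cox model for any arm, and a sparse dose level is left out of the model.

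The only other onset analysis named is that "the Kaplan-Meier method will be used to produce graphical presentation of the survival curves by treatment group". The SAP text names no log-rank, exact or penalised test as a replacement. Meaningful relief and unconfirmed perceptible relief "will be analyzed in the same way as described for time to onset of" confirmed perceptible relief, so the conditions carry over to them.

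**The concern.** A minimum event count is a sensible guard for a Cox model that also carries site and sex terms. The difficulty is what happens below the minimum: the SAP removes the comparison when it could change the method. One sparse arm, placebo, cancels all five comparisons. Placebo is sparse when few placebo subjects report relief within 6 hours, and that is the setting in which an effective drug would stand out most.

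Confirmed perceptible relief is "defined as the time to onset of perceptible pain relief for those subjects who had meaningful pain relief". If everyone with meaningful relief also stopped the perceptible watch, confirmed perceptible and meaningful relief have the same event count, and both would lose their comparison together.

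At stake is the only planned test and effect estimate for a secondary endpoint. A test chosen after unblinding to fill the gap would carry little weight.

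**Working it through.** **Inputs from the documents.** Arm sizes are 44 for placebo and Dose Levels 1 to 4, and 22 for Dose Level 5 (SAP Table 7-1): 5 × 44 + 22 = 242, the stated total. These follow from 40 and 20 evaluable subjects with 10% withdrawal (40/0.9 = 44.4; 20/0.9 = 22.2). Onset follow-up is 6 hours (SAP 9.3.2.1). The threshold is 5 events, which is 5/44 = 11.4% of a large arm and 5/22 = 22.7% of Dose Level 5. The plan states no power, event count or expected rate for onset, so there is no onset figure to reproduce. All rates below are assumptions.

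**Step 1. How often the placebo rule applies.** P(X ≤ 4) for X ~ Binomial(44, p):

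| Assumed placebo rate by 6 h | P(no Cox model) |
|---|---|
| 5% | 93% |
| 10% | 55% |
| 15% | 19% |
| 20% | 4.4% |
| 25% | 0.7% |

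**Step 2. What can go untested.** Take placebo at 4/44, the highest count that triggers the rule. Two-sided Fisher exact p against a 44-subject active arm is 0.051 at 12/44, 0.029 at 13/44 and 0.0002 at 20/44. So any 44-subject arm with 13 or more events differs from placebo at the 5% level and is still not compared.

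**Step 3. Effect on power.** For 44 versus 44, all pairs of counts were enumerated with exact binomial weights and the Fisher test was applied at two-sided 5%. The second column sums over every pair. The third counts only pairs with at least 5 placebo events, as the SAP requires.

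| Placebo / active rate | Every trial tested | Under the SAP rule |
|---|---|---|
| 10% / 40% | 87.9% | 34.5% |
| 15% / 40% | 68.0% | 49.6% |
| 20% / 40% | 44.8% | 40.6% |

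A log-rank simulation gives the same pattern: 92.8% versus 38.0%, 77.4% versus 58.0% and 54.4% versus 50.0%. It used 10,000 trials, exponential onset after an assumed 0.75 h lag, and non-events at risk to 6 h.

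**Step 4. The active-arm rule on its own.** It matters separately only when placebo has at least 5 events. An excluded 44-subject arm then has at most 4/44 against at least 5/44, which does not favour VX-150. For Dose Level 5 the most favourable excluded result is 4/22 versus 5/44, with Fisher p = 0.47. Even if all four active events come before any placebo event, with no earlier censoring, the log-rank z is only 0.89. Exclusion is nevertheless fairly likely: P(fewer than 5 of 22) is 54%, 32%, 16.5% and 2.7% at true rates of 20%, 25%, 30% and 40%.

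**Step 5. Does the proposed fallback work?** At 10% / 40%, a log-rank test stratified by sex and an assumed 2, 4 or 8 sites has simulated power of 92.8%, 92.4% and 92.7% (4,000 trials each). Type I error of the unstratified test, 44 versus 44, was 5.3% at a 10% rate and 4.8% at 20%.

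**The case against.** The strongest reply is that this is a guard on a secondary analysis with low stakes. Much of that stands.

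- SAP 9.1 makes no multiplicity adjustment outside MCP-Mod, so every onset P value is nominal, across five doses in a Phase 2B trial. A fallback test would be nominal too.
- At placebo rates of 20% or more the rule seldom applies and costs little power. The documents do not say which rate to expect, so they do not show that the rule would apply.
- A reader might infer that the SAP contradicts the Protocol. It does not: Protocol 12.3 leaves analysis details to the SAP. The SAP narrows the planned analysis.
- A reader might infer that all onset information is lost. The Kaplan-Meier curves do not depend on the count, and unconfirmed perceptible relief, which has at least as many events, may still be testable.
- A reader might see the exclusion of the small Dose Level 5 arm as the main harm. Step 4 shows that, with at least 5 placebo events, this half cannot hide a significant result in favour of VX-150. It costs an imprecise estimate and makes inclusion in the model depend on outcome.
- The wording for the other two onset variables is most naturally read as using each variable's own count, so it is not a defect of weight.

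The reply does not explain why a sparse placebo arm should end the comparison when a standard test can still be run.

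**Conclusion.** The point holds for the placebo rule. As written, fewer than 5 placebo events removes all five dose-versus-placebo comparisons of a stated secondary endpoint, however large the observed difference, and leaves curves only. The loss is large at an assumed placebo rate of 10% (power 87.9% falling to 34.5% against a 40% active rate), moderate at 15% and small at 20%. It is therefore material only if the placebo rate is about 15% or less, and the documents do not settle whether it is. The active-arm rule is a minor matter. Importance is low to moderate, and the primary analysis is untouched.

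**What to change.** Keep the 5-event minimum for the Cox model. Add one prespecified fallback: when placebo, or the dose being compared, has fewer than 5 events on the onset variable being analysed, compare that dose with placebo by a log-rank test stratified by site and sex. Report Kaplan-Meier estimates for all six arms, as the Protocol plans.

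The cost is a few SAP sentences and standard software, with no new data. The change should be made before database lock. There are downsides. Sparse arms get no adjusted hazard ratio and have low precision. If only an active arm is sparse, two methods are used across doses. No test helps if neither arm has any events. The P values stay nominal.
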